APPENDIX 1-4 FOOTNOTES

AE = adverse event; ALT = alanine transaminase; ANC = absolute neutrophil count; aPTT = activated partial thromboplastin time; AST = aspartate transaminase; BUN = blood urea nitrogen; CBC = complete blood count; Cr = creatinine; CRP = C-reactive protein; CT = computed tomography; D = Day; DLT = dose-limiting toxicity; ECG = electrocardiogram; ECOG = Eastern Cooperative Oncology Group; eCRF = electronic case report form; EOS = End-of-Study; F/U = follow-up; Hgb = hemoglobin; HIV = human immunodeficiency virus; IFN = interferon; LDH = lactate dehydrogenase; MRI = magnetic resonance imaging; NCI CTCAE = National Cancer Institute Common Terminology Criteria for Adverse Events; PD = progressive disease; PD-1 = programmed death receptor-1; PD-L1 = programmed death-ligand 1; PT = prothrombin time; Q3W = every 3 weeks; RECIST = Response Evaluation Criteria In Solid Tumors; RNA = ribonucleic acid; SAE = serious adverse event; TSH = thyroid stimulating hormone; UNS = unscheduled visit/Safety Follow-up Visit; WBC = white blood cell; WOCBP = women of childbearing potential.

Screening ^a	Routine laboratory tests (serum chemistry, hematology) for screening should be performed within 28 days prior to enrollment or can be obtained from a standard of care visit within 28 days of first dose of pembrolizumab. Laboratories obtained within 7 days of Day 1 visit, with the exception of a CBC with ANC, do not need to be repeated on Day 1.
24-hour postdose visit ^b	The window for 24-hour postdose visit is ± 3 hours.
DLT Assessment Period ^c	DLT assessment period is Study Day 1 through Study Day 29.
Extended Pembrolizumab Treatment ^d	During Extended Pembrolizumab Treatment, pembrolizumab will be administered Q3W with standard of care procedures performed by the site. Data related to dosing, concomitant medications, AEs, and SAEs must be entered in the CRF.
EOS / Safety FU ^e	After a patient is discontinued from both trial treatments, a mandatory EOS/Safety Follow-up visit will be performed 28 (± 3) days after the last administration of trial treatment, regardless of the reason for permanent discontinuation.
UNS ^f	A UNS should be performed if there is suspected disease progression or patient safety concerns. Procedures for the visit are at the discretion of the investigator according to local standard of care guidelines. All disease assessments will be performed as per local standard of care guidelines. Confirmation of disease progression by repeat imaging is not mandatory.
Demographics/Medical history/Prior medications ^g	Medical history includes clinically significant diseases, surgeries, cancer history, response to cancer treatment, and all medications (eg, prescription drugs, over the counter drugs, herbal/homeopathic remedies, nutritional supplements) used by the patient within 28 days prior to the Screening Visit. Baseline melanoma and HNSCC disease status, histology, stage and molecular profiling of genetic alterations or mutations (if available) will be recorded. Prior treatment includes treatment for the primary diagnosis, including prior systemic, radiation treatment and surgical treatment. Results of any prior genetic screening tests and any immunohistochemical (IHC) tests, such as for PD-L1, will also be recorded. The date of last prior cancer treatment must be documented. Radiographic studies performed prior to trial entry may be collected for review by the investigator.
Vital signs ^h	Includes oral temperature (only at trial injection visits), heart rate, respiratory rate, systolic and diastolic blood pressure, and pulse oximetry.
Physical examination ⁱ	The investigator or qualified designee will conduct physical examinations. A complete physical examination is conducted at Screening and EOS, and a targeted physical examination (based on interval history and/or AEs) including assessment of superficial lesions is conducted at all other visits per the Schedule of Trial Events.
12-Lead ECG ^j	Electrocardiogram (12-lead ECG) should be performed at Screening, after treatment on Days 15 and 29, and at EOS in Phase 1, and collected at Screening only in Phase 2.

APPENDIX 1-4 FOOTNOTES (CONT'D)

Review AEs ^k	In Phase 1, assessments of injection-site reactions will be collected for a minimum of 90 minutes through the first 4 weekly injections and for 30 minutes following the remaining injections of SD-101 at the clinical site. Injection-site reactions will be graded based on the Toxicity Grading Scale for Healthy Adult and Adolescent Volunteers Enrolled in Preventive Vaccine Clinical Trials (Appendix 5). In Phase 2, injection-site reactions that persist for more than 7 days will be recorded as AEs. All other AEs and laboratory safety measurements will be graded per NCI CTCAE Version 4.03. All AEs, whether gradable by CTCAE or not, will also be evaluated for seriousness. AEs will be collected through 28 days after the last dose of trial treatment.
Concomitant medications ^l	All concomitant medications taken by the patient from Screening through the EOS visit will be reported.
HIV and hepatitis testing ^m	Serum hepatitis B, hepatitis C, and HIV testing as determined by laboratory tests for HBsAg, anti-HBc, and anti-HBs; anti-HCV; and anti-HIV -1/2, respectively. For HNSCC patients only, HPV status (positive + or negative) at Screening will be determined from either archival test results or new testing.
Serum chemistry and CRP ⁿ	Per local standard of care at the discretion of the investigator.
Hematology ^o	Per local standard of care at the discretion of the investigator.
Coagulation ^p	Per local standard of care at the discretion of the investigator.
Thyroid function tests ^q	Per local standard of care at the discretion of the investigator.
Pregnancy testing ^r	For WOCBP, serum or urine pregnancy test must be negative within 72 hours prior to the first trial treatment. If the urine test is positive or cannot be confirmed as negative then a serum test is required which must be negative for the patient to enroll. Dipstick can be used. Additional pregnancy testing should be scheduled per local regulations where applicable. All female patients are considered to be WOCBP except if they have been postmenopausal for at least 2 years or surgically sterile for at least 1 year.
Blood for IFN-alpha inducible gene expression (pharmacodynamic) ^s	Phase 1 Dose Escalation Cohorts 1-4 only: IFN-inducible gene expression measured at pre-dose on Day 1 (baseline), at Day 8 prior to injection, and at Day 9 which is 24 hours after injection.

APPENDIX 1-4 FOOTNOTES (CONT'D)

Diary card issuance and/or review ^{bb}	Prior to each of the first 4 initial weekly doses of SD-101 in Phase 1, patients will receive a new Diary Card with instructions to measure and record local injection- site reactions and solicited AEs that occur post SD-101 injection. Note that injection-site reactions are not required to be recorded separately on the AE eCRF unless the duration is greater than 7 days. The completed Diary Cards will be reviewed with the patients at their next study visit.
SD-101 Post-treatment observation (minimum 90 minutes) ^{cc}	Patients will remain in clinic for 90 minutes after each of the first 4 weekly SD-101 injections in their first course and for 30 minutes after subsequent injections.
Tumor biopsies (consent required) ^{dd}	
Tumor biopsy of Lesion A will be performed within 28 days prior to the first dose of SD-101. Two samples are required at each time point. See specific guidance for samples in Section 10.1.2. Lesion A should be of a sufficient size such that the intratumoral biopsy does not compromise the investigator’s ability to assess the lesion size changes per RECIST over time. Biopsies may be obtained via punch, core needle, or surgical excision. Biopsies should be limited to readily accessible tumor lesions (eg, skin; peripheral lymph nodes). (See specific guidance for minimum needle gauge in the Study Reference Manual). Collections are to be done pre- injection on treatment days and may occur pre-injection on treatment days or within the visit window prior to treatment. Repeat samples may be required if adequate tissue is not provided. Details of tumor biopsy procedures including processing and shipping are provided in the study laboratory manual. Biopsies will be collected on:
 
 • Phase 1 Dose Escalation Cohorts 1-4 only: Screening, Days 29, 85 and 169 visits. • Phase 2 Dose Expansion Cohorts 1 and 3 only: Screening, Days 50, 106, and Day 190 visits. • Phase 2 Dose Expansion Cohorts 2 and 4 to 8 only: Screening, Days 29, 85, and Day 169 visits.
Day 9 and Day 30 visits ^{ee}	These visits are for HNSCC patients in Phase 2 Dose Expansion: Cohort 3 on Day 30, and Cohorts 4, 6 and 7 only on Day 9.

APPENDIX 5: TOXICITY GRADING SCALE FOR HEALTHY ADULT AND ADOLESCENT VOLUNTEERS ENROLLED IN PREVENTIVE VACCINE CLINICAL TRIALS

Local Reaction to Injectable Product	Mild (Grade 1)	Moderate (Grade 2)	Severe (Grade 3)	Potentially Life Threatening (Grade 4)
Pain	Does not interfere with activity	Repeated use of non-narcotic pain reliever > 24 hours or interferes with activity	Any use of narcotic pain reliever or prevents daily activity	Emergency room (ER) visit or hospitalization
Tenderness	Mild discomfort to touch	Discomfort with movement	Significant discomfort at rest	ER visit or hospitalization
Erythema/Redness ^a	2.5 – 5 cm	5.1 – 10 cm	> 10 cm	Necrosis or exfoliative dermatitis
Induration/Swelling ^b	2.5 – 5 cm and does not interfere with activity	5.1 – 10 cm or interferes with activity	> 10 cm or prevents daily activity	Necrosis

Source: ([Center for Biologics Evaluation and Research 2007](#)).

^a In addition to grading the measured local reaction at the greatest single diameter, the measurement should be recorded as a continuous variable.

^b Induration/swelling should be evaluated and graded using the functional scale as well as the actual measurement.

APPENDIX 6: RECIST V1.1 AND IMMUNE-RELATED RECIST RESPONSE DEFINITION

NOTE: As of Amendment 9, this Appendix is for information only. Use of the guidelines outlined within is at the discretion of the investigator and is not mandatory. All disease response assessments, including the timing, type, and evaluation of imaging, are to be performed and assessed at the investigator's discretion per local standard of care. Confirmation of progression by repeat imaging is not mandatory. Decisions on treatment discontinuation should be made per investigator based on local standard of care. All imaging will be performed as per local standard of care guidelines.

Assessments will use RECIST v1.1 guidelines ([Eisenhauer, Therasse et al. 2009](#)), which are included in the Study Reference Manual, and study specific modification of the RECIST v1.1 guidelines referred to as irRECIST.

RECIST v1.1

Baseline selection of lesions

All lesions are measured by long axis and short axis (perpendicular to the long axis). At baseline, all tumor lesions are identified as either target lesions or non-target lesions and will be evaluated at baseline and every post-baseline imaging time point.

Target lesions: Minimal size of 1.0 cm by long axis unless a lymph node which must be a minimal size of 1.5 cm by short axis. Superficial lesions must measure at least 10 mm in long diameter and be measurable by calipers to qualify as target lesions. Maximum target lesions are 5 with a maximum of 2 lesions per organ representative of all involved organs.

Non-target lesions: Radiographically visible but do not meet size qualification of target lesions. Lymph nodes must measure at least 1.0 cm by short diameter to qualify as non-target lesions (if smaller considered non-pathologic). Excess target lesions (> 5 overall or 2 per organ) are followed as non-target lesions.

Baseline measurement of lesions

At baseline, the sum of the long diameters of all target lesions (5 lesions total with maximum of 2 lesions per organ representative of all involved organs), is calculated. The sum is referred to as the SOD for the baseline time point. All other lesions should be identified as non-target lesions and be recorded at baseline.

Post-baseline radiographic response assessment

At each post-baseline imaging time point, the long axis diameter of all target lesions is measured and recorded. A response of the target lesions is assessed by determination of the overall SOD of the lesions (SOD for that imaging time point). A response for each baseline non-target lesion is determined and recorded. The presence of any new lesions is recorded (of note a lymph node must measure at least 1.0 cm by short axis diameter to qualify as a pathologic lesion).

Target lesion response

Complete response (CR): disappearance of all target lesions. Any pathological lymph nodes (whether target or non-target) must have reduction in short axis to < 10 mm.

Partial response (PR): At least a 30% decrease in the SOD of target lesions, taking as reference the baseline SOD.

Progressive disease (PD): At least 20% increase in the SOD of target lesions, taking as reference the smallest prior SOD in the trial (this includes the baseline sum if that is the smallest in the trial). In addition to the relative increase of 20%, the sum must also demonstrate an absolute increase of least 5 mm.

Stable disease (SD): Neither sufficient shrinkage to qualify for PR nor sufficient increase to qualify for PD, taking as reference the smallest SOD while in the trial.

Non-target lesion response assessment

Complete response (CR): Disappearance of all non-target lesions and normalization of tumor marker level. All lymph nodes must be non-pathological in size (<10 mm short axis).

Non-CR/Non-PD: Persistence of 1 or more non-target lesion(s) and/or maintenance of tumor marker level above the normal limits.

Progressive disease (PD): Unequivocal progression of existing non-target lesions. (Note: the appearance of 1 or more new lesions is also considered progression).

New lesion assessment

At each post-baseline imaging time point, an evaluation of the presence of new lesions (yes/no) is made. The lesions are recorded as new lesions and not target or non-target lesions.

Lymph nodes must be a new lesion and measure at least 10 mm by short diameter to qualify as a new lesion overall response assessment.

A lesion identified on a follow-up study in an anatomical location that was not scanned at baseline is considered a new lesion.

Overall response assessment

Overall response assessment is based on target lesion response, non-target lesion response and new lesions and is listed in [Table 1](#) below.

Table 1: Overall Response Definitions Using RECIST v1.1

Target Lesions	Non-target Lesions	New Lesions	Overall Response
CR	CR	No	CR
CR	Non-CR/non-PD	No	PR
CR	Not evaluated	No	PR
PR	Non-PD or not all evaluated	No	PR
SD	Non-PD or not all evaluated	No	SD
Not all evaluated	Non-PD	No	NE
PD	Any	Yes or No	PD
Any	PD	Yes or No	PD
Any	Any	Yes	PD

Source: ([Eisenhauer, Therasse et al. 2009](#))

CR = complete response; NE = not evaluable; PD = progressive disease; PR = partial response; SD = stable disease.

Immune-related RECIST

irRECIST is a modification of RECIST v1.1 which requires confirmation of initial PD per RECIST v1.1 with an additional scan obtained at least 4 weeks later that also meets the criteria of PD progression per RECIST v1.1. In determining whether or not PD is confirmed per irRECIST, the investigator should consider all target and non-target lesions as well as any incremental new lesion(s).

The following are scenarios where PD is confirmed at repeat imaging if ANY of the following occurs by irRECIST:

- Tumor burden remains $\geq 20\%$ and at least 5 mm absolute increase compared to nadir
- Non-target disease resulting in initial PD is qualitatively worse
- New lesion resulting in initial PD is qualitatively worse

- Additional new lesion(s) since last evaluation
- Additional new non-target progression since last evaluation

The following are scenarios where PD is not confirmed at repeat imaging if ALL of the following occur by irRECIST:

- Tumor burden is $< 20\%$ or < 5 mm absolute increase compared to nadir
- Non-target disease resulting in initial PD is stable or qualitatively improved
- New lesion resulting in initial PD is stable or qualitatively improved
- No incremental new lesion(s) since last evaluation
- No incremental new non-target progression since last evaluation

The rationale of the modification is to address observed *pseudoprogression* as well as late responses that are expected with immunotherapy. Guidance for continued imaging and treatment following an initial determination of PD per RECIST v1.1 is provided in the protocol in Section [10.4.1](#).

APPENDIX 7: IMAGING MODALITIES

NOTE: As of Amendment 9, all post-baseline imaging is to be performed according to local standard of care. The modality, anatomic areas, and timing of imaging is at the discretion of the investigator. This section has been updated accordingly.

Contrast enhanced CT (preferred) or enhanced MRI are the preferred imaging modalities to be used. Chest x-rays performed during the Screening phase (and repeated at any time during the trial if clinically indicated) may be used as supportive data, as an accessory to the chest CT scans.

All imaging data are to be collected on film or in digital format.

CT/MRI of the Chest/Abdomen/Pelvis

CT/MRI imaging of the chest, abdomen, and pelvis is required at Screening, regardless of the location of known metastases. For HNSCC, imaging of the neck is also required. In addition, CT/MRI scans must be obtained of anatomic regions not covered by the chest, abdomen and pelvic scans, in patients where there is clinical suspicion of malignant disease/metastases. Such additional CT/MRIs will be required at Screening only when malignant disease/metastases is known/suspected.

Brain MRI/CT

Brain scans (MRI or CT) are required at Screening. Brain scans should be conducted during the course of the trial if the Screening scan was positive as clinically indicated.

Non-radiographic Assessments/Digital Photography

These should be made at the sites and recorded in the source documents at the time points indicated in Appendix 1 through Appendix 4. Visible skin lesions should be measured clinically and documented digitally using standardized photographic images, including a ruler for scale as part of the image. Superficial lesions not well captured by imaging scans should be documented using standardized photographic images, including a ruler for scale as part of the image to track the lesion size.

Image Acquisition Guidelines

Similar methods of tumor assessment and similar techniques must be used to characterize each identified and reported lesion at baseline. Image acquisition guidelines should be consistent with the American College of Radiology imaging guidelines and local imaging guidelines. All

measurable and non-measurable lesions should be assessed at Screening and at any tumor assessment time points indicated as mandatory in Appendix 1 through Appendix 4. Additional assessments may be performed, as clinically indicated, if there is a suspicion of progression or for confirmation of response. The investigator will base response to treatment on local assessment guidelines. Imaging-based evaluation is preferred to physical examination. Helical (spiral) CT scans of chest, abdomen and pelvis are preferred. If not available, conventional (non-helical, non-spiral CT) should be used.

Intravenous contrast should be used for all CT scans. Oral contrast should be used for CT abdomen and pelvis. If intravenous contrast is contraindicated, CT may be performed without contrast. If oral contrast is indicated, milk or other suitable substitution per local imaging standards may be used. CT scan of the chest is preferred compared to MRI of the chest.

However, for patients who cannot receive intravenous contrast, MRI may be used as an alternative imaging modality. Intravenous imaging agent (gadolinium or acceptable alternative per local institutional standards) should be used for all MRI scans. Patients who develop contrast allergy after trial enrollment may be followed by MRI for subsequent tumor measurements or have non-contrast CT scans per approval by a Dynavax Medical Monitor and per institutional standard practice. Sections should be contiguous, similarly sized and consistent from

visit-to-visit. Section thickness must be based on institutional standards (eg, from 5 to 8 mm; 10 mm cuts are not recommended). Chest x-ray, ultrasound, and positron emission tomography scans are not acceptable methods to measure baseline disease status for the purposes of this trial.

RP2D	recommended Phase 2 dose
SAE	serious adverse event
SAP	statistical analysis plan

Abbreviation or Term	Definition
MedDRA	Medical Dictionary for Regulatory Activities

Approved

1.0 INTRODUCTION

This statistical analysis plan contains definitions of analysis populations and endpoints, outlines the timing of statistical analyses, and provides a comprehensive description of statistical analyses to be implemented to assess the safety, tolerability, biologic activity, and preliminary efficacy of SD-101 in combination with pembrolizumab as described in Protocol DV3-MEL-01 (Amendment 8: 08 February 2018): “A Phase 1b/2, Open-label, Multicenter, Dose escalation and Expansion Trial of Intratumoral SD-101 in Combination With Pembrolizumab in Patients With Metastatic Melanoma or Recurrent or Metastatic Head and Neck Squamous Cell Carcinoma (HNSCC)”.

Due to strategic changes, only some of the objectives will be evaluated. Those objectives not evaluated will be *italicized* and annotated as “*(not implemented)*”, where applicable, throughout this SAP; statistical methods for these objectives are also not described. The main text of this SAP covers only assessment of the objectives by data contained in the clinical database. Pharmacodynamic assessment will be described in an annex to this SAP. Pharmacodynamic objectives will also be annotated.

Groupings of patients to be used in the analyses are also changed from what were described in the protocol, based on the knowledge accumulated through the conduct of the trial.

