The SD-101 doses selected are based on the mechanism of action, results of nonclinical and previous clinical studies conducted with SD-101 (DV3-HNV-01, DV3-HCV-01), and an ongoing trial of SD-101 in low-grade lymphoma (DV3-LYM-01). Based on data from a trial in healthy normal male volunteers (DV3-HNV-01), elevation of IFN- α inducible genes was seen after a single 0.1 mg subcutaneous dose and increased with doses up to 5 mg. AEs were limited to flu-like symptoms and administration-site pain and induration. For further information, see the Investigator's Brochure.

The starting dose of SD-101 (2.0 mg intratumorally) was chosen based on safety data from the DV3-LYM-01 study and in consideration that the safety profile of SD-101 given together with pembrolizumab is unknown. A lower dose of SD-101 1.0 mg was added in Amendment 4 of this protocol to determine optimal dosing and not because of a safety concern. With Amendment 5, 8.0 mg was selected as the RP2D and another RP2D of 2.0 mg was selected for testing in Amendment 6. The rationale for modifying the SD-101 dose to 2.0 mg/lesion is based on preliminary internal data which suggest that overall objective response could potentially double when dosing at 2.0 mg as compared with 8.0 mg per lesion. Furthermore, increasing the number of tumor lesions for injection may enhance priming of neoantigen-specific anti-tumor T-cells to address potential tumor heterogeneity at different tumor locations. Selection of a 2.0 mg per injection permits injection in up to 4 lesions/regions to reach a maximum of 8.0 mg dose per subject, the highest total dose cleared based on Phase 1b.

Based on the preliminary results for PD-1/PD-L1 naive patients in the ongoing Phase 1b/2 DV3-MEL-01 (SYNERGY-001) study, the number of patients who are resistant/refractory to anti-PD1/PD-L1 therapy was expanded in Amendment 8 to further evaluate 2.0 mg-dosing of SD-101.

The dose of pembrolizumab chosen for this study (200 mg Q3W) is the dose currently recommended in both monotherapy and combination studies with pembrolizumab.

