12.4 Trial Analysis Populations

The safety population will include all enrolled patients who receive at least 1 dose of both pembrolizumab and SD-101. The primary analysis population for the study will include the safety population with separate analyses for Phase 1 Dose Escalation and each Phase 2 Dose Expansion cohort. The efficacy population will comprise all patients who receive at least 1 dose of both pembrolizumab and SD-101 and who have baseline and at least 1 post-baseline imaging assessment. The ITT population will include all enrolled subjects regardless of having a post-baseline radiographic assessment. Additional subpopulations for an exploratory and retrospective analysis may include PD-L1 status (positive or negative [ie, < 1% positivity]) and specific prior anti-PD-1/PD-L1 therapy. Further details of statistical considerations will be provided in a separate Statistical Analysis Plan.

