The trial population includes a total of approximately 284 men and women with at least 1 site of disease that qualifies as a target lesion per RECIST v1.1 and is accessible for intratumoral injection.

Phase 1 Dose Escalation Cohorts 1-4 will include up to 24 patients with metastatic melanoma who are anti-PD-1 naïve or experienced.

Phase 2 Dose Expansion will include approximately 160 patients with metastatic melanoma and approximately 100 patients with recurrent or metastatic HNSCC:

- 1) Expansion Cohort 1 of approximately 60 melanoma patients who are anti-PD-1/L1 naïve
- 2) Expansion Cohort 2 of approximately 25 melanoma patients who have disease progression on anti-PD-1/L1 therapy
- 3) Expansion Cohort 3 of approximately 25 HNSCC patients who are anti-PD-1/L1 naïve
- 4) Expansion Cohort 4 of approximately 25 HNSCC patients who have disease progression on anti-PD-1/L1 therapy
- 5) Expansion Cohort 5 of approximately 25 melanoma patients who are anti-PD-1/L1 naïve
- 6) Expansion Cohort 6 of approximately 25 HNSCC patients who are anti-PD-1/L1 naïve
- 7) Expansion Cohort 7 of approximately 25 HNSCC patients who are refractory or resistant to anti-PD-1/L1 therapy
- 8) Expansion Cohort 8 of approximately 50 melanoma patients who are refractory or resistant to anti-PD-1/L1 therapy.

Some of these study groups will be rearranged for final analysis as analysis groups based on tumor indications, anti-PD-1/L1 experience, and dose of SD-101.

Phase 1 results will be presented for each of the 4 dose groups.

Results for Phase 2 objectives, using combined Phases 1 and 2 data, will be presented by 2mg/lesion and 8mg/lesion doses for

- MEL/NAIVE: metastatic melanoma patients who are anti-PD-1/L1 naïve, including
 - subjects in Phase 1 2mg and 8mg groups
 - subjects in Phase 2 Cohort 1 (both 2mg/lesion and 8mg single lesion) and Cohort 5 (2mg/lesion)
- MEL/EXP: metastatic melanoma patients who are anti-PD-1/L1 experienced, including
 - subjects in Phase 1 2mg and 8mg groups
 - subjects in Phase 2 Cohort 2 (both 2mg/lesion and 8mg/lesion) and Cohort 8 (2mg/lesion)
- HNSCC/NAIVE: HNSCC patients who are anti-PD-1/L1 naïve, including
 - subjects in Phase 2 Cohort 3 (both 2mg/lesion and 8mg/lesion) and Cohort 6 (2mg/lesion)
- HNSCC/EXP: HNSCC patients who are anti-PD-1/L1 experienced, including
 - subjects in Phase 2 Cohort 4 (both 2mg/lesion and 8mg/lesion) and Cohort 7 (2mg/lesion)

2.1 Phase 1

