In Expansion Cohort 8, approximately 50 metastatic melanoma patients who are refractory or resistant to anti-PD-1/L1 therapy will be enrolled. If 13 or more responses are observed, the 95% exact confidence interval will yield a lower bound of no less than 15.0%.

In Expansion Cohort 3, approximately 25 anti-PD-1/L1 naïve HNSCC patients will be enrolled. The null hypothesis that the response rate is < 20% will be tested against a 1-sided

alternative at a significance level of 0.05. The design will provide greater than 80% power if the true response rate is $> 40\%$. There will be no adjustments for multiplicity.

In Expansion Cohort 6, approximately 25 anti-PD-1/L1 naïve HNSCC patients will be enrolled. This will allow a preliminary estimate of the response rate associated with the dose and dosing schedule chosen for Expansion Cohort 6. If 9 or more responses are observed, the 95% exact confidence interval will yield a lower bound of no less than 20%.

In Expansion Cohort 4, approximately 25 HNSCC patients who have disease progression on anti-PD-1/L1 therapy will be enrolled. The null hypothesis that the true response rate is 5% will be tested against a 1-sided alternative and will be rejected if 4 or more responses are observed. This design yields a type I error rate of 0.05 and 80% power when the true response rate is 21%. There will be no adjustments for multiplicity.

In Expansion Cohort 7, approximately 25 HNSCC patients who are refractory or resistant to anti-PD-1/L1 therapy will be enrolled. This will allow a preliminary estimate of the response rate associated with the dose and dosing schedule chosen for Expansion Cohort 7. If 4 or more responses are observed, the 95% exact confidence interval will yield a lower bound of no less than 5%.

Although changes to the groupings for the final analysis will be made, there is no impact to the sample size calculation, as all analyses will be descriptive. At some places in above sample size calculation one-sided significance level of 0.05 was referenced, to standardize the analyses, two-sided significance level of 0.05 is used throughout. Power and 95% exact confidence interval descriptions are still applicable if the underlying conditions in various analysis groups hold.

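### The SAP replaces the planned cohort-by-cohort Phase 2 response rates with post hoc dose pools, adds Phase 1 patients to the melanoma pools, and leaves Cohorts 1 and 5 with no ORR of their own

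*SAP*

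**What the plan says.** Protocol 12.4 makes the safety population the primary analysis population, with "separate analyses for Phase 1 Dose Escalation and each Phase 2 Dose Expansion cohort". Protocol 12.2 and SAP 5.0 justify the Phase 2 sample sizes cohort by cohort, each with its own power statement, cutoff or confidence bound.

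SAP 1.0 announces the change: "Groupings of patients to be used in the analyses are also changed from what were described in the protocol, based on the knowledge accumulated" while the trial was running. SAP 2.0 then says: "Results for Phase 2 objectives, using combined Phases 1 and 2 data, will be presented by 2mg/lesion and 8mg/lesion doses for" four groups: MEL/NAIVE, MEL/EXP, HNSCC/NAIVE and HNSCC/EXP. Both melanoma groups include "subjects in Phase 1 2mg and 8mg groups"; the HNSCC groups list no Phase 1 patients. MEL/EXP also includes "subjects in Phase 2 Cohort 2 (both 2mg/lesion and 8mg/lesion) and Cohort 8 (2mg/lesion"). SAP 9.6, 9.6.1 and 9.11 name only these analysis groups for Phase 2 output. SAP 5.0 adds that "there is no impact to the sample size calculation, as all analyses will be descriptive".

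On dose choice, protocol 4.1.1.2 lists efficacy among the data used to select the RP2D. Protocol 2.8 bases the later 2 mg choice on preliminary internal data suggesting that "overall objective response could potentially double when dosing at 2.0 mg as compared with 8.0 mg per lesion". Protocol 2.6 likewise reports higher efficacy at 2 mg per lesion in naïve patients.

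**The concern.** The new groups were drawn after open-label results were available, and the SAP says that accumulated knowledge shaped them. Three problems follow.

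- **Re-use.** If Phase 1 responses helped to choose a dose, counting those patients again in the Phase 2 estimate for that dose carries any favourable chance result forward.
- **Mixing.** The MEL/NAIVE 2 mg column puts together patients with different entry criteria, schedules and numbers of injected lesions.
- **Loss of the planned estimates.** ORR is the Phase 2 primary endpoint. Cohort 1 was the largest cohort, and Cohort 5 opened at Amendment 6, when 2 mg per lesion was selected. Cohort 5 is therefore the naïve-melanoma group enrolled after that choice, yet no planned row shows it alone.

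The exact interval around a pooled rate reflects binomial sampling only. It corrects neither selection nor mixture.

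**Working it through.** **1. The plan's own figures.** Exact binomial, from the inputs in SAP 5.0:

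- Cohort 1, n = 60, null 35%, one-sided 0.05: the smallest r with P(X ≥ r | 0.35) ≤ 0.05 is 28. Type I error is 0.041 and power at 55% is 92.3% (stated: above 90%).
- Cohort 2, at least 6 of 25: type I error 0.033, power at 30% is 80.7% (stated: 80%).
- Cohort 4, at least 4 of 25: type I error 0.034, power at 21% is 80.1% (stated: 80%).

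These figures reproduce, and they belong to whole cohorts. Cohort 1's 92.3% describes 60 patients in one row, and no such row is planned.

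**2. Who is in the MEL/NAIVE 2 mg column** (protocol 4.1.1, 4.1.2.1, 5.1 and 7.1):

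| Source | Lesions injected | SD-101 start | SD-101 doses | Target lesions required |
|---|---|---|---|---|
| Phase 1, 2 mg | 1 | Day 1 | up to 11, one course | 1, with the 10 mm minimum waived if superficial |
| Cohort 1, 2 mg part | 2 to 4 | Day 22 | up to 22, two courses | 2 |
| Cohort 5 | 1 to 4 | Day 1 | up to 20, one course | 2 |

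Cohort 1's dose follows from the number of lesions selected (8 mg for one, 2 mg each for two to four). Splitting it by dose therefore also splits it by number of injected lesions.

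**3. The other columns, if dosing followed the protocol.** Protocol Tables 4-3 and 4-4 give Cohorts 2, 3 and 4 8.0 mg only, and Cohorts 6, 7 and 8 2.0 mg per lesion or injection. Then:

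- HNSCC/NAIVE 8 mg and 2 mg are exactly Cohorts 3 and 6.
- HNSCC/EXP 8 mg and 2 mg are exactly Cohorts 4 and 7.
- MEL/EXP 8 mg is Cohort 2 plus Phase 1; MEL/EXP 2 mg is Cohort 8 plus Phase 1.

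SAP 2.0, however, describes Cohorts 2, 3 and 4 as containing both doses. If so, their estimates are broken up as well, and Cohort 2 patients join Cohort 8.

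**4. Phase 1 share.** With s Phase 1 patients and n Phase 2 patients, share = s/(s + n). Phase 1 planned 3 to 6 per dose, naïve and experienced together, so s = 6 in one stratum is an upper limit (before the optional 6 further patients at the RP2D):

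- MEL/NAIVE 2 mg: 6/(6 + 25) = 19% with Cohort 5 only; 6/(6 + 85) = 7% if all 60 of Cohort 1 were at 2 mg.
- MEL/EXP 2 mg: 6/(6 + 50) = 11%.
- MEL/EXP 8 mg: 6/(6 + 25) = 19%.
- HNSCC: 0.

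**5. Size of the re-use effect.** The documents give no response rates by dose, so this rests on assumptions: true ORR 30% at all doses, 6 Phase 1 patients per dose, the best observed of k doses chosen, and the excess spread evenly over the two experience strata. With F the Binomial(6, 0.30) distribution function, the expected best count is Σ[1 − F(x)^k] over x = 0 to 5.

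- k = 2: 2.415 responses against 1.8 expected; (2.415 − 1.8)/6 = +10.2 points in the selected Phase 1 group.
- k = 4: 2.961 responses; (2.961 − 1.8)/6 = +19.4 points.

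Pooled shift = that excess × s/(s + n), in percentage points:

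| s | n | best of 2 | best of 4 |
|---|---|---|---|
| 3 | 25 | +1.1 | +2.1 |
| 6 | 25 | +2.0 | +3.7 |
| 3 | 85 | +0.4 | +0.7 |
| 6 | 85 | +0.7 | +1.3 |

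The range is about +0.4 to +3.7 points. Cohort 1's split between doses is not stated. If the MEL/NAIVE 8 mg column held fewer than 25 Phase 2 patients, its Phase 1 share could exceed 19%.

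**The case against.** The change is disclosed, the pools are listed, and Phase 1 is also reported separately by dose. No hypothesis test is planned. Protocol 12.1 says only that cohort data may be reported separately, and protocol 12.0 already requires the CSR to explain changed methods and identify post hoc exploratory analyses. Since Amendment 9 Phase 2 response is no longer collected, and protocol 8.2.1.1 says ORR may be analysed from earlier data. The computed shifts are small beside exact intervals at these sample sizes. All this stands and limits the weight of the point. It does not supply the missing cohort rows, and the SAP does not label the pools post hoc.

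Four stronger readings are tempting, and the documents do not support them.

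- **That no planned cohort estimate survives.** Under protocol dosing the four HNSCC columns are Cohorts 3, 6, 4 and 7. SAP 6.3 also says that Phase 2 analyses follow *study groups*, the term SAP 2.0 uses for the cohorts, and SAP 2.0 rearranges only some of them. That conflicts with 9.6, so the SAP is inconsistent rather than uniformly silent on cohorts.
- **That MEL/EXP blends the different eligibility of Cohorts 2 and 8 into one rate.** Results are split by dose, and under protocol dosing the two cohorts fall in different columns.
- **That upward bias is established.** Efficacy informed dose choice, but the patients behind the 2 mg decision are not identified. Cohort 1 was open before Amendment 6 and may have contributed. Bias is plausible, and its size is assumed.
- **That the inflation could reach about 5 points.** Under this model that takes about 20 earlier patients at each of four doses, against 3 to 6 per dose planned in Phase 1.

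**Conclusion.** The point holds for the melanoma groups. By the SAP's own account the grouping is post hoc, and it departs from protocol 12.4. Cohorts 1 and 5 lose their own ORR, and Cohorts 2 and 8 are each pooled with Phase 1 patients who entered under different lesion criteria. Under the assumptions shown, re-use of Phase 1 patients adds about 0.4 to 3.7 points to a melanoma pool and nothing to an HNSCC pool. That range covers Phase 1 re-use only, not mixture and not any part Cohort 1 played in choosing 2 mg, so dropping Phase 1 patients may not remove all selection. The HNSCC columns, and the separation of Cohort 2 from Cohort 8, are sound only if Cohorts 2 to 4 were dosed as the protocol describes; SAP 2.0 says otherwise. Calling the analyses descriptive answers the question of testing, not what each ORR estimates. This should be corrected, though it does not invalidate the trial.

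**What to change.** - In SAP 9.6 and 9.11, make the Phase 2 primary presentation ORR with its 95% Clopper-Pearson interval for each protocol expansion cohort (1 to 8), without Phase 1 patients. This also shows Cohort 5 alone.
- Keep the dose pools as supportive tables, labelled post hoc, shown with and without Phase 1 patients.
- Reconcile SAP 6.3 (*study groups*) with SAP 9.6 (*analysis groups*).
- Reconcile the dose descriptions of Cohorts 2, 3 and 4 in SAP 2.0 with protocol Tables 4-3 and 4-4, and state how many patients in each cohort fall in each dose column.

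The cost is extra rows in the efficacy tables and wider intervals per cohort. No new data are needed.
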